14 DATA MANAGEMENT
15 DIRECT ACCESS TO SOURCE DATA/DOCUMENTS32
16 ETHICAL AND REGULATORY CONSIDERATIONS
17 DISSEMINATION OF RESULTS
18 REFERENCES

APPENDIX 1: STUDY RISK ASSESSMENT35	

1 ABBREVIATIONS

Abbreviation	Description
Ag-RDTs	Antigen Rapid Diagnostic Tests
AE	Adverse event
ADE	Adverse Device Effect
API	Application Programming Interface
AI	Artificial Intelligence
ATS	Asymptomatic Testing Site
CFR	Case Report Form
DHSC	Department of Health and Social Care
EC	Ethics Committee (see REC)
GCP	Good Clinical Practice
GDPR	General Data Protection Regulation
LFD	Lateral Flow Device
MHRA	Medicines and Healthcare products Regulatory Agency
NHSD	National Health Service Digital
RDT	Rapid Diagnostic Test
REC	Research Ethics Committee
SAE	Serious Adverse Event
SADE	Serious Adverse Device Effect
UADE	Unanticipated Adverse Device Effect
UON	Unique Organisation Number

2 BACKGROUND AND RATIONALE

Severe acute respiratory syndrome coronavirus 2 (SARS-CoV-2) is a betacoronavirus responsible for coronavirus disease-19 (COVID-19)¹. Assessment of the extent of infection has largely been based on real-time polymerase chain reaction (RT-PCR) that identifies the virus in those with an active or recent infection. However, in the UK, antigen testing is predominantly performed in those presenting with symptoms (which may represent a small fraction of those infected with SARSCoV-2) and it cannot detect past infection. Moreover, it has been reported that early estimates of 80% of the infections being asymptomatic were overestimated, and such figures were subsequently revised to 17-20%².

Historically, a test has always been considered a support for clinical diagnosis, not a substitute, and to this extent the timing of the infection and the viral load at time of test are variables that should be considered in the overall assessment. Recent evidence demonstrated that 60% of infected individuals without symptoms were undetected, of which more than 1/3 had a high enough viral load to represent a high risk of infection to others³.

LFDs are relatively easy-to-use rapid test that can be performed at home settings by lay user or near the point of care, without the need for laboratory infrastructure or expensive equipment. There are two types of SARS-CoV-2 LFDs: SARS-CoV-2 virus antigen(s) tests, and antibody tests that detect one or more types of antibodies produced by the host immune response against the virus.

Preliminary results conducted by a Joint PHE Porton Down and the University of Oxford⁴ study showed that performance characteristics of such LFD appear to be good with a low failure rate with a demonstrated specificity of 99.6%. A joint University of Liverpool / DHSC pilot demonstrated that the accuracy of self-read LFDs was lower than those read by trained operatives.

Most SARS-CoV-2 antigen LFDs require nasal and/or oral fluids samples. A key step of the entire testing strategy that this study is intending to address and research is the mechanism of reporting the LFD results. This is typically read by the individual performing the test and in this study scenario, such individual would need to input the result of the test following the LFD manufacturer's test interpretation instructions, manually into the process flow (by answering a question in the digital test reporting service).

DHSC and NHSD intend to enhance the existing Self-Test LFD service, (using an Innova device – purchased by DHSC and MHRA derogated for lay person use (MHRA ref. number: DEU/012/2020/003) and accessed from the gov.uk website)) with additional functionality. In order to render the interpretation of the test less subjective and less prone to user error and to decrease the risk of falsification of reported results, it is proposed to use an AI based technology that will request the user take a picture of the test result. The above process will allow the user to submit their LFT result via the camera on a mobile device and for the result interpretation to be made digitally by AI reader technology and for the result to be returned to the user.

This Performance Evaluation Study is aiming to collect data to verify the performance claims under the anticipated conditions of use.

The whole Performance Evaluation Study will be split into two parts – Sub-studies, which will be run in parallel.

Sub-study 1 (source: ATS photos) – Image collection which were captured in Asymptomatic Test Sites (ATSs). LFT will be performed as per manufacturer's IFU. Then the fully trained operative will read the test results, take a photo of completed test and enter/upload results on NHSD web service as per written instruction. The picture of completed test will be taken at the point at which the result is interpreted/decided.

The main objective of this Sub-study is to test and validate that AI algorithm can meet the primary objective analytical performance measures detailed in Section 3.

Sub-study 2 (source: photos from NHS and ASC users) - Antigen Lateral Flow Device (LFD) test subjects who have identified themselves as working within NHS primary care (GP's, NHS dentistry, community pharmacists and NHS optometrists etc), or are linked to a subset of adult social care homes (staff, visitors and visiting professionals) will be invited to take images on their mobile devices (such as mobile phone or tablet) and upload these images using the NHSD web service. Study participants will be self-tested using an Innova LFT device (on naseal swab samples) – purchased by DHSC and MHRA derogated for lay person use (MHRA ref. number: DEU/012/2020/003) and accessed from the gov.uk website)). Self-testing will be performed as per manufacturer's instructions for use (IFU). Non-Innova LFT devices will be removed from the data set analysed.

The picture of completed test will be taken at the point at which the result is interpreted/decided.

The main objectives of this Sub-study is to test and validate that the digital service and integrated AI algorithm which wll be used by subjects can meet the observational objectives measures detailed in Section 3.

This performance evaluation study will use AI technology (provided by a third party) to interpret the results of LFD tests from photos. Study participants in Sub-study 2 submit their photo when they register and report a test result. This performance evaluation study will test the hypothesis that a digital reader will:

• Facilitate and, in some cases, improve consistency and accuracy of result interpretation compared to a self-read test.

• potentially identify more positive results in asymptomatic subjects than a human read.

In addition to above, this performance evaluation study will improve our understanding of the use of the online "photograph taking process" in practice and to determine whether the product is easy to use and safe in the intended context of use.

Figure 1: Self-Test – Logical Architecture

If the algorithm is found to be at least as good as the average user read, this evidence will support an application to MHRA to allow the use of the algorithm to help the user interpret tests for mass testing, using the same LFD self-test digital service.

3 To assess the effectiveness and efficiency of the digital service in its intended use setting by the intended user population (reference to the SIU	3) At least 95% of effectiveness and efficiency will confirm the usability of the image-capture element of the digital service, regardless of the device used for			
	image capture (i.e., phone, tablet)			
4) To assess the performance of the				
algorithm in identifying void tests (i.e.	1) The 9/ of tests reported as youd by			
tests performed incorrectly) where a	4) The % of tests reported as void by			
tests performed incorrectly), where a	the algorithm will be compared to the %			
control line is missing.	reported by individuals as void (study			
	participants will be asked to submit photos			
	of void tests. In addition, where there is a			
	discrepancy (whereby the user's response			
	differs from an algorithm's read, these will			
	be referred to an independent off-line			
	review of the image. The % of those			
	images correctly identified as yoid will be			
	reported			
	reponea.			

5) To assess the implication of the types of devices used (Tablets, PCs, phones of various models) on the image quality and therefore implication for algorithms	5) A breakdown of the device types, with % of images which meet the quality requirements defined above, particularly linked to image quality (resolution, pixels, lighting/flash)

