1.6 User checks all answers and reports result

Participants

Participants for the trial will be recruited from two use case groups:

- Adult Social Care
- Primary Care (Community pharmacy, NHS Optometry, NHS Dental and General Practice)

Methodology

A survey will be distributed via comms teams to the use case groups to be completed during the trial period.

This survey will collect data on the participant's themselves and their experience of using the product during the trial, as well as operate as a recruitment tool for qualitative interviews.

Interviews to be conducted with 15 participants from each use case group (Adult Social Care and Primary Care) who consent to be contacted for a follow-up interview. The interview will cover their survey responses in more depth, and to attempt to establish the root cause of any user errors or difficulties encountered.

Adobe analytics will also be used to identify user interactions across the digital journey, including any drop off points.

Survey Questions

User Profile

- Sector of work
- Job Title
- Context of Use
- Gender
- Age
- Ethnicity
- Internet Use
- Accessibility software used
- Disabilities or long-term health conditions

Usability Questions

- How many Covid-19 Lateral Flow tests have you taken so far during the trial? (If you are a nominated person responsible for reporting all staff lateral flow test results, please tell us how many test results you have reported in total)
- Of these, how many times did you take and upload a photo of the lateral flow test strip?
- If you did not take and upload a photo every time, please tell us why
- Did you ever have to try more than once to take and upload a photo?
- How many times did you have to try more than once?
- If you had to try more than once, at any time, please tell us more about what happened
- How easy did you find it to take and upload a photo of the lateral flow test strip?

Interview Script

Welcome and Intro

- Purpose
- Consent and confidentiality
- Recording
- Observers

Recap

Refer back to their survey answers for prompts:

- Can you tell me a little bit about how you found taking and uploading a photo of your test?
- What device did you use?
- Where were you when you were taking the test/taking the photo?
- How did you approach it?
- Did you experience any difficulties doing this?
- Did you need to get any help or assistance from anyone else?

Improvements

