- What benefits (if any) do you see in taking a photo of the lateral flow strip and uploading it?
- If you were to do this process again in the future, would you take a photo of the test strip on those occasions?
- If not, why not?
- How might we improve the process of taking and uploading a photo of the lateral flow test device?

Usability Metrics

The ISO 9241-11 standard defines usability as "the extent to which a product can be used by specified users to achieve specified goals with effectiveness, efficiency and satisfaction in a specified context of use".

The ISO/IEC 9126-4 Metrics recommends that usability metrics should include:

- Effectiveness: The accuracy and completeness with which users achieve specified goals
- Efficiency: The resources expended in relation to the accuracy and completeness with which users achieve goals.
- Satisfaction: The comfort and acceptability of use.

Usability Metrics for Effectiveness

a) Completion Rate

Effectiveness can be calculated by measuring the completion rate – uploading image of the completed LFD test. Referred to as the fundamental usability metric, the completion rate is calculated by assigning a binary value of '1' if the test participant manages to complete a task and '0' if he/she does not.

Effectiveness can thus be represented as a percentage by using this simple equation:

$$Effectiveness = \frac{\text{Number of tasks completed successfully}}{\text{Total number of tasks undertaken}} \times 100\%$$

Our aim for a completion rate of at least 95%

b) Number of Errors

This measurement involves counting the number of errors the study participant makes when attempting to take and upload the image.

Usability Metrics for Efficiency

Efficiency is measured in terms of submitted image quality. The Efficiency rate is calculated by assigning a binary value of '1' if the uploaded image was successfully interpreted by AI, and value of '0' will be assigned if AI failed to interprets the image.

Efficiency can be represented as a percentage by using this simple equation:

Efficiency = Number of images successfully analysed by AI X 100%

Total Number of images submitted for AI interpretation

Our aim for an efficiency rate of at least 95%

Usability Metrics for Satisfaction

a) Task Level Satisfaction

After users attempt a task (irrespective of whether they manage to achieve its goal or not), they will be given a questionnaire so as to measure how difficult that task was.

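### One pooled 95% rate cannot confirm that image capture is usable on every device, as outcome 3 claims

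*Protocol*

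**What the plan says.** Section 3 sets the criterion for objective 3, which concerns the intended users in the intended setting. The pass mark is 95% for both measures, and the conclusion drawn from it is worded: "efficiency will confirm the usability of the image-capture element of the digital service, regardless of the device used for". The sentence ends by naming the devices it has in mind, "image capture (i.e., phone, tablet".

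Appendix 2 defines the two measures under its usability metrics.

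- **Effectiveness** is the completion rate, scored by "assigning a binary value of '1' if the test participant manages to complete a task and '0' if he/she does not". It continues: "Effectiveness can thus be represented as a percentage by using this simple equation". The denominator is "Total number of tasks undertaken". The aim is at least 95%.
- **Efficiency** is the number of images the AI managed to interpret, divided by all images sent to it. The aim is again at least 95%.

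Neither formula has a term, split or minimum for device. The only output by device is outcome 5 in Section 3: "A breakdown of the device types, with % of images which meet the quality requirements defined above". It has no threshold. Objective 5 lists tablets, PCs and phones, while outcome 3 names only phone and tablet.

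Section 12 states that no separate statistical analysis plan is in use.

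**The concern.** The conclusion in outcome 3 is about every device, but the quantity that triggers it is an average over devices. When one device class supplies most of the uploads, the average is close to that class's rate and says little about the others. The rule can then confirm usability for any device while one class performs badly.

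The protocol itself treats device as relevant. Objective 5 exists to examine its effect on image quality and hence on the algorithm, and one quality criterion in Section 3 is a minimum vertical resolution of 1920 pixels, which plausibly depends on the camera.

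What is at stake is the wording of a conclusion. Section 12.2 makes effectiveness and efficiency the main measures of Sub-study 2, and Section 17 sends the results to the regulator. A device-independent statement could enter that submission without evidence for the less common devices.

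**Working it through.** **The plan's own figure.** The 95% is a chosen target. No sample size, interval or device mix stands behind it, so there is nothing to reproduce. What can be checked is which device-specific rates the rule lets through.

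**Inputs from the protocol:** the 95% threshold (Section 3 and Appendix 2) and the pooled denominators (Appendix 2). Section 12.2 instead describes efficiency through time to completion. A 95% threshold fits only the Appendix 2 definition, so that one is used here.

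**Assumed inputs**, because the documents give none: tablet share of uploads *s*, phone success rate *p*₁, tablet success rate *p*₂.

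**Step 1, pooled rate.**

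pooled = (1 − *s*) × *p*₁ + *s* × *p*₂

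- *s* = 5%, *p*₁ = 97%, *p*₂ = 60%: 0.95 × 0.97 + 0.05 × 0.60 = 0.9215 + 0.0300 = 0.9515. Pass.
- 900 phone uploads at 97% and 100 tablet uploads at 80%: (873 + 80) / 1,000 = 0.953. Pass.

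**Step 2, the lowest tablet rate at which the pooled rate still reaches 95%.**

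*p*₂ = (0.95 − (1 − *s*) × *p*₁) / *s*

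For *s* = 10% and *p*₁ = 97%: (0.95 − 0.873) / 0.10 = 0.77.

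| Phone rate | Tablets 5% of uploads | 10% | 20% | 50% |
|---|---|---|---|---|
| 96% | 76% | 86% | 91% | 94% |
| 97% | 57% | 77% | 87% | 93% |
| 98% | 38% | 68% | 83% | 92% |

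At a 2% tablet share with phones at 97%, tablets could fail every time and the rule would still pass: 0.98 × 0.97 = 0.9506. With equal shares the masking is small, at most three percentage points below target in this table. The problem grows as the minority share shrinks and as the majority rate rises above 95%.

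The same identity applies separately to effectiveness (tasks) and efficiency (images), so requiring both to reach 95% does not remove the problem.

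**Step 3, whether outcome 5 closes the gap.** Outcome 5 counts images that meet the Section 3 quality criteria. Efficiency counts images the AI interpreted, and effectiveness counts completed tasks. These are related but different quantities, and outcome 5 has no pass mark. A poor result for tablets there would leave the outcome 3 conclusion unchanged.

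**The case against.** **The sentence may mean 95% on whichever device is used.** It does not say that one overall rate is formed, and the Appendix 2 formulas could be computed for any subset. That reading is possible, but the stated denominators are all tasks and all submitted images, and no analysis by device of either measure is described. If the clause means only that devices are combined, the result is an average and says nothing about any one device. Either way the text needs correcting.

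**A failing device would probably be seen.** Appendix 2 links efficiency to image quality, and the quality criteria are meant to make images readable by the algorithm. Poor tablet images would therefore probably show in outcome 5. Failed attempts are reported by point in the journey, drop-off is tracked, and interviewees are asked which device they used. All this stands as a way of noticing a problem, but none of it enters the criterion.

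**The consequence is limited.** Appendix 2 calls both figures aims, the proposal to go live in Section 12.1.4 depends on sensitivity and specificity, and the risk table promises a further post-market usability study. This stands: the point does not touch the accuracy objective.

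**A stronger inference to avoid.** Appendix 2's survey contains the parenthesis "If you are a nominated person responsible for reporting all staff lateral flow test results, please tell us how many test results you have reported". A reader might infer that a few practised reporters could carry the 95% while most ordinary users fall short. The documents do not support that as a finding. They give neither the number of such reporters nor their success rate, Appendix 2 covers professional as well as lay users, and success per task is the measure the protocol chose. A criterion based on first uploads would answer a different question. It might also not be computable, because Section 14 creates the subject identifier only on submission and describes no lasting user key.

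**Conclusion.** The concern holds for devices. As written, outcome 3 can confirm usability on any device from a pooled rate that one device class fails by a wide margin. With phones at 97%, tablets could be as low as 57%, 77% or 87% when they supply 5%, 10% or 20% of uploads. These figures rest on assumed shares and rates and show only what the rule allows. A reader might infer that tablets are expected to fail or that the study will reach a wrong conclusion. Nothing in the documents says so.

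This should be corrected because it changes what may be concluded from Sub-study 2 and is cheap to correct. It does not undermine the pooled rates themselves, which remain valid averages over the devices observed.

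**What to change.** In outcome 3 and Appendix 2, do one of the following.

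1. **Report by device class.** Give the AI-interpretation rate separately for phone and tablet, and for PC if it is accepted. Give the completion rate the same way where device type is captured for failed attempts. Limit the usability claim to classes that each reach 95%, and keep the pooled rate as a supporting figure.
2. **Narrow the claim.** Delete the clause that extends the conclusion to any device, and state the result as an average over the observed device mix, with that mix shown.

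If nominated reporters can be identified, a descriptive table for them is reasonable, but it should not enter the criterion.

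**Cost.** Option 2 is a wording change. For option 1, outcome 5 already needs device type for images received, so efficiency by device is a tabulation. Completion by device also needs device type for abandoned or failed attempts, which the documents do not show to be recorded.

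Rare device classes will have wide intervals, and the claim may become narrower. As a guide, suppose the sponsor wanted to show a rate above 95% within a class by an exact one-sided 2.5% test with at least 80% power. That would take about 851 uploads if the true rate is 97%, 338 if 98% and 173 if 99%. The test level, power and true rates are assumptions, and repeat uploads by the same person would raise the numbers. The protocol's own rule asks only that the rate reach 95%, so these sizes are not a condition of the fix.

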4 STUDY DESIGN AND PROCEDURE

This Performance Evaluation Study is aiming to collect data to verify the performance claims under the anticipated conditions of use.

The whole Performance Evaluation Study will be split into two parts – Sub-studies, which will be run in parallel.

Sub-study 1 (source: ATS photos) – Images captured in Asymptomatic Test Sites (ATSs). LFT will be performed as per manufacturer's IFU. Then the fully trained operative will read the test results, take a photo of completed test and enter/upload results using a NHSD web service as per written instructions. The picture of completed test will be taken at the point at which the result is interpreted/decided.

The images will be analysed by the AI algorithm which will return an interpreted result. This result will be stored in the NHSD image store.

Sub-study 2 (source: photos from NHS and ASC users) - Antigen Lateral Flow Device (LFD) test subjects who have identified themselves as working within NHS primary care (GP's, NHS dentistry, community pharmacists and NHS optometrists etc), or are linked to a subset of adult social care homes (staff, visitors and visiting professionals) will be invited to take images on their mobile devices (such as mobile phone or tablet) and upload these images using the NHSD web service. Study participants will be self-tested using an Innova LFT device (on naseal swab samples) – purchased by DHSC and MHRA derogated for lay person use (MHRA ref. number: DEU/012/2020/003) and accessed from the gov.uk website)). Self-testing will be performed as per manufacturer's instructions for use (IFU). The picture of completed test will be taken at the point at which the result is interpreted/decided.

The webservice for Sub-study 2 is written in React.j and is capable of processing requests from various types of mobile devices. The webservice will allow the user to use their device's camera to take a photograph of their LFD and submit this to NHSD. Upon receipt of the image, it is written to an image store prior to being processed and analysed by the vendors' Al component.

The Al's interpretation is then passed to a results database where is it logged alongside the test subject's own asserted result.

When an void result is observed (no control line), the study participant will be instructed to take another test with a new test kit. Study subjects will be asked to take a picture of the void test before proceeding with a new test.

Al interpreted result will not be returned to the user during either sub-study, but instead analysed and kept as evidence to assess the accuracy of the algorithm reading against the reported outcome by the lay user and trained operator.

During this study we have an intention collecting data from four (A, B, C and D) different variations of Innova device (see Figure 2 below).

Figure 2: Four variations of Innova device

In addition to the manually read and AI generated results, a third-party independent inspection will be performed for a subset of images to create a 'most trusted' result against which the sensitivity and specificity of the AI read can be measured and to demonstrate the effectiveness of the AI algorithm, showing that it is 'at least as good as the average user read'. This will be performed for both sub-studies.

The samples to be reviewed by the independent inspectors will fall into two categories. Firstly, all samples where there is a discrepancy between the AI result and the test subjects reported result.

Secondly, a random sample of images where there is consensus between all the results (human and AI). This will be a selection of 10% of the consensus positives alongside at least 50 consensus negatives per week.

Assessment will take place via interpretation of the submitted image of the test subjects LFD. Each inspector will individually assess the image and record their interpretation of the result against the unique image identifier. The individual assessments will subsequently be compared to determine a consensus amongst the inspectors and a final 'third party review' data point will be recorded against the unique image identifier.

Note that this data point may not represent a unanimous view amongst the three inspectors, but will be a majority view at least. On a daily basis the results of each individual assessment and the 'third party review' data point will be provided to the AI vendor and to DHSC for review.

These individual inspectors should be experienced in making clinical assessments and understand the rigour required in order to achieve a reliable outcome. To perform the assessment, 3 individuals shall be trained by interpreting a practice suite of images, recording their verdicts and comparing these to determine a consensus view. Each individual will require an internet connected computer which is able to receive the images to be assessed from the AI vendor and return their results to the AI vendor and to DHSC.

Sub-study 2 procedure ilustrated in Flowchart 1 below.

Flowchart 1: Sub-study 2 process flow

